5.4 Chart Review for Withdrawn Subjects

Subjects who are withdrawn from the study during the follow-up phase due to AEs/SAEs will no longer follow the study visit schedule nor participate in study-specific procedures. These subjects have the option to consent and allow for continued monitoring by medical and radiographic record review through the end of the two-year Extended Follow-up Phase. Subjects who are withdrawn from the study also have the option to enroll in a separate LTFU observational study.

6 STATISTICAL CONSIDERATIONS

6.1 Primary Endpoint

The primary endpoint is safety, and will consist of the rate of AEs/SAEs in anterior VBT surgery.

6.2 Secondary Endpoints

The secondary endpoint is feasibility, as determined by the ability to successfully implant the investigational device in study subjects.

6.3 Statistical Methods

6.3.1 Baseline Data

Baseline and demographic characteristics will be summarized by standard descriptive summaries (e.g. means and standard deviations for continuous variables such as age and percentages for categorical variables such as sex). Categorical data analysis methods such as chi-square will be used for dichotomous variables and t-test for continuous data (such as differences in Cobb angle). Logistic regression analysis will be conducted to analyze various factors associated with adverse events in the anterior tethering surgical procedure.

6.3.2 Safety Analysis

The safety endpoint will be factors associated with the adverse events in patients that have undergone anterior VBT surgery. Variable reporting for adverse event will be dichotomous. Descriptive statistics will be used to report number and type of adverse events. Further, chi-square or Fisher's-exact test analysis will be used to identify variables that correlate with adverse events following anterior tethering surgery. Further, logistic regression will be conducted to clarify which variables are associated with adverse outcomes. Odds ratio along with confidence intervals will be reported.

All subjects will begin the safety analysis at Study Day 0 (day of surgery). Intraoperative and post-intervention medical events or signs and symptoms of the complications arising after the start of study intervention will be captured using list of common events associated with anterior VBT surgery. Adverse signs, symptoms, and/or laboratory abnormalities already existing prior to the baseline visit will be captured in the medical history assessment. The date of onset, severity, and end date (if relevant) will be documented.

Medical events resulting from any procedure performed in the study will be collected as adverse events (AEs). The event description, date of onset, end date, severity, and outcome will be documented for the study-related AEs. The frequencies of AEs by type, body system, severity and relationship to study intervention will be summarized. SAEs (if any) will be described in detail. A distinction will be made between those AEs/SAEs which are “device-related”, those which are “not device-related”, and those which are “uncertain to be related”. “Device-related” complications will include any events directly related to the integrity, safety, or biomechanics of the Anterior Vertebral Tether Device composed of the investigational staples, screws, locking caps, and PET cord. Device-related AE incidence will be summarized along with the corresponding exact binomial 95% two-sided confidence intervals.

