8.3 Definition of an Adverse Event

An adverse event is any untoward medical occurrence in a subject who has received an intervention (drug, biologic, or other intervention). The occurrence does not necessarily have to have a causal relationship with the treatment. An AE can therefore be any unfavorable or unintended sign (including an abnormal laboratory finding, for example), symptom, or disease temporally associated with the use of a medicinal product, whether or not considered related to the medicinal product.

We will use the Clavien-Dindo Classification system [47], as well as the Comprehensive Complication Index (based off of the Clavien-Dindo system) [48] to classify and analyze patient adverse events. **Grade I and Grade II events will be considered AEs. (See Appendix 1 for classification table)**

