12 APPENDIX

12.1 Appendix 1: Clavien-Dindo complications classification system (from Dindo, *et al.*)

TABLE 1. Classification of Surgical Complications

Grade	Definition
Grade I	Any deviation from the normal postoperative course without the need for pharmacological treatment or surgical, endoscopic, and radiological interventions Allowed therapeutic regimens are: drugs as antiemetics, antipyretics, analgetics, diuretics, electrolytes, and physiotherapy. This grade also includes wound infections opened at the bedside
Grade II	Requiring pharmacological treatment with drugs other than such allowed for grade I complications Blood transfusions and total parenteral nutrition are also included
Grade III	Requiring surgical, endoscopic or radiological intervention
Grade IIIa	Intervention not under general anesthesia
Grade IIIb	Intervention under general anesthesia
Grade IV	Life-threatening complication (including CNS complications)* requiring IC/ICU management
Grade IVa	Single organ dysfunction (including dialysis)
Grade IVb	Multiorgan dysfunction
Grade V	Death of a patient
Suffix "d"	If the patient suffers from a complication at the time of discharge (see examples in Table 2), the suffix "d" (for "disability") is added to the respective grade of complication. This label indicates the need for a follow-up to fully evaluate the complication.

*Brain hemorrhage, ischemic stroke, subarachnoidal bleeding, but excluding transient ischemic attacks.
CNS, central nervous system; IC, intermediate care; ICU, intensive care unit.

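### Sections 8.3 and 8.4 promise to analyse adverse events by Clavien-Dindo grade and the Comprehensive Complication Index, but 6.3.2 tests factors on an undefined yes/no variable and Section 6 uses neither scale

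*Combined protocol and SAP*

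**What the plan says.** Section 6.1 sets the primary endpoint: "The primary endpoint is safety, and will consist of the rate of AEs/SAEs in anterior VBT surgery". Section 6.3.2 words it differently: "The safety endpoint will be factors associated with the adverse events in patients that have undergone anterior VBT surgery". It then fixes the form of the variable, "Variable reporting for adverse event will be dichotomous", and says that chi-square or Fisher "test analysis will be used to identify variables that correlate with adverse events following anterior tethering surgery", followed by logistic regression with odds ratios and confidence intervals. No cut for the yes/no variable and no list of factors is given.

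The same section also plans description: "The frequencies of AEs by type, body system, severity and relationship to study intervention will be summarized", and "SAEs (if any) will be described in detail". Device-related AE incidence gets an exact binomial 95% interval.

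Section 8.3 says the study will use the Clavien-Dindo system "as well as the Comprehensive Complication Index (based off of the Clavien-Dindo system) [48] to classify and analyze patient adverse events", and 8.4 repeats this. Grades I and II count as AEs, Grades III to V as SAEs. Appendix 1 opens Grade I with "Any deviation from the normal postoperative course without the need for pharmacological treatment" and places blood transfusion in Grade II. Neither scale appears anywhere in Section 6.

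**The concern.** The protocol commits to a graded measure of complications and then specifies an inferential analysis that ignores it. An analyst following 6.3.2 would never compute the index; one following 8.3 and 8.4 would find no method for it.

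The choice matters because of where the cut may fall. If yes means any AE, a child with one Grade I event and a child with a Grade IV event get the same value, and the commoner the events, the fewer children are left on the no side to compare. The factor tests would then say little about which children have serious complications. As 6.3.2 calls those factors the safety endpoint, this is more than a side analysis in that section's own terms.

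**Working it through.** **The plan's own power figure.** The only one is in 6.4: more than 80% for paired t-tests at n = 40, two-sided 5%. The noncentrality is (difference/SD) × √40: thoracic 17.9/6.6 × 6.325 = 17.2; lumbar 6.5/5.38 × 6.325 = 7.6. Both give power above 99.99%, so the statement is true. It concerns curve measurements and says nothing about AEs. I carry the two-sided 5% level over to the safety tests as an assumption.

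**Exact bound for the yes/no outcome.** Take 40 subjects, a factor splitting them 20/20, and *k* event-free children. The most extreme table puts all *k* in one group, with two-sided Fisher p = 2 × C(20,k)/C(40,k).

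| k event-free | smallest possible p |
|---|---|
| 2 | 0.487 |
| 3 | 0.231 |
| 4 | 2 × 4,845/91,390 = 0.106 |
| 5 | 2 × 15,504/658,008 = 0.047 |

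Fewer than 5 event-free children therefore rules out p<0.05. Section 6.3.2 also allows chi-square. Uncorrected, k = 4 gives 40 × (4×20 − 16×0)²/(20×20×4×36) = 4.44, p = 0.035, but the expected count is then 2 per group, where Fisher would normally be used.

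**Power, graded against binary.** The documents give no AE rate, factor prevalence or effect size, so all of these are assumed. The split is 20/20. The graded outcome is a Mann-Whitney test on worst grade (4,000 simulated trials per cell), standing in for the index.

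| Any-AE rate | Odds ratio | Graded | Fisher, any AE | Chi-square, any AE |
|---|---|---|---|---|
| 50% | 3 | 43% | 26% | 37% |
| 80% | 3 | 46% | 16% | 27% |
| 95% | 3 | 44% | 1% | 5% |
| 50% | 5 | 73% | 54% | 67% |
| 80% | 5 | 79% | 39% | 51% |
| 95% | 5 | 76% | 3% | 10% |

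At an odds ratio of 2 the graded test has 20-22% power and Fisher 1-11%. Part of the gap to Fisher is that test's conservatism, but the graded outcome also beats the uncorrected chi-square in every row.

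**Two explicit grade mixes** (none/I/II/III+, 20 per group, 8,000 simulated trials, rerun for this check):

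- 10/45/35/10% against 5/20/40/35%: any AE by Fisher 2%, Grade III+ by Fisher 36%, rank test on grade 60%.
- 20/45/25/10% against 5/25/35/35%: 17%, 36% and 71%.

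The first mix favours the graded test by construction. Its any-event odds ratio is (0.95/0.05)/(0.90/0.10) = 2.1, while its Grade III+ odds ratio is (0.35/0.65)/(0.10/0.90) = 4.8. In the second mix the two are close: (0.95/0.05)/(0.80/0.20) = 4.75 against 4.8.

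**The case against.** **Severity is not discarded.** A reader might infer that the safety analysis as a whole loses it. The documents do not support that: 6.3.2 tabulates AEs by severity and describes SAEs in detail, 6.1 names the AE/SAE rate as primary, 8.3 and 8.4 separate AE from SAE by grade, and the stopping rules in 6.6 rest on SAEs. This stands, and it confines the loss to the factor tests. The severity table is no substitute there: it counts events rather than each child's burden, and 8.5 records intensity as mild, moderate or severe, not by grade.

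**The cut and the event rate are assumed.** A reader might infer that nearly every child will be a yes. No AE rate is given, and a chest tube is a planned step of the operation (1.2.3), so having one is not in itself a deviation. The yes/no variable might also mean SAE, device-related AE or each listed event. This stands: what the text shows is an undefined cut, and the near-empty outcome is conditional.

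**Low power is mostly the sample size.** The synopsis calls the analysis primarily descriptive, and 6.4 concedes that the study is not powered for significance. A reader might infer that the yes/no outcome can detect hardly any factor. That is too strong: at any-AE rates of 30-70% and an odds ratio of 10, Fisher's power is 83-87%. Dichotomising is the main cause of low power only when almost all children have an event.

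**Section 8 is not strictly contradicted.** Tabulating by severity is compatible with analysing by grade in a loose sense. But the index is named for analysis and has no analysis.

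**Conclusion.** The point holds in limited form. It follows from the text alone that Section 6 never uses either of the two scales promised for analysis, that the factor tests use a binary outcome with no stated cut, and that 6.3.2 and 6.1 word the safety endpoint differently.

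The size depends on assumptions. The bound of 5 event-free children is exact for Fisher with a 20/20 split. If yes means Grade I or higher, the graded outcome gains 17 percentage points of power over Fisher at an odds ratio of 3 and an AE rate of 50% (43 − 26), and 43 points at a rate of 95% (44 − 1). Against the uncorrected chi-square the gains are 6 and 39 points. The graded outcome had more power in every scenario simulated, but it does not rescue the factor analysis at this sample size: power remains below 50% at odds ratios of 3 or less. The change is worth making because the plan already promises grading and the cost is small.

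**What to change.** In 6.3.2, replace the sentence that makes the AE variable dichotomous, as follows:

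1. **Graded summary.** For each subject, report the highest Clavien-Dindo grade and the Comprehensive Complication Index over Day 0 to POD 90, the period in which 8.5 records all AEs, with median and range.
2. **Factor analyses.** Use one of these two as the outcome (rank test, or ordinal or linear regression), and label the analyses exploratory.
3. **One binary outcome.** Keep SAE yes/no with an exact 95% interval through POD 730, alongside the planned device-related AE incidence. The 90-day graded outcome cannot do this job alone: 6.6.2 diagnoses tether failure after 3 months, and the synopsis places over-correction, implant failure and re-operation in the extended phase. With 4 of 40 subjects, for example, the exact interval would be 2.8% to 23.7%.
4. **Endpoint wording.** Reconcile the safety endpoint in 6.3.2 with the AE/SAE rate in 6.1.
5. **Data capture.** Make sure the CRF records the grade. The event fields in 8.5 list intensity but neither the grade nor the index.

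The cost is SAP wording plus a CRF check, with a possible added field. The small downside is that differences in grade or index are less familiar to readers than odds ratios.

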6.4 Sample Size and Power

The purpose of this study is to longitudinally follow a cohort of patients treated with a novel use of an implanted device, referred to as the Anterior Vertebral Tether Device, to explore safety and feasibility of the implant. Based on device implantation in up to 40 subjects, the study will not be sufficiently powered to gain statistical significance. However, this preliminary study will allow some insight into the safety of implantation, as measured by the acceptability of adverse events, as well as feasibility of implantation, as estimated by the proportion of successful implants of the Anterior Vertebral Tether Device. The regulatory status of such an implant requires that the Sponsor obtains an IDE. There is no active comparative group in this limited study. Notably, there is a useful comparator group from review of published data (historical controls) and from the data of the Harms Study Group (CHOP IRB# 06-005052), for which the Sponsor has access. A comparative analysis will be performed combining data from this clinical trial with IRB# 06-005052 to evaluate patient factors and clinical outcomes depending on the intervention received. Data from this clinical trial will not be shared with IRB# 06-005052.

Using data observing pre and post thoracic and lumbar measurements for a small sample of subjects; for the thoracic measurements, a sample size of 40 will have >80% power to detect a difference in means of 17.9, assuming a standard deviation of differences of 6.6, using a paired t-test with a 5% two-sided significance level. For the lumbar measurements, a sample size of 40 will have >80% power to detect a difference in means of 6.5, assuming a standard deviation of differences of 5.38, using a paired t-test with a 5% two-sided significance level. Sample size calculations were performed using NQuery software.

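### The adverse-event logistic regression in up to 40 subjects has no small-sample method or predictor limit, so its odds ratios may not exist if events are rare or near universal

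*Combined protocol and SAP*

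**What the plan says.** Section 6.3.1 states that "Logistic regression analysis will be conducted to analyze various factors associated with adverse events in the anterior tethering surgical procedure". Section 6.3.2 repeats the commitment: "logistic regression will be conducted to clarify which variables are associated with adverse outcomes". It adds "Odds ratio along with confidence intervals will be reported". The outcome is binary: "Variable reporting for adverse event will be dichotomous". For single factors, "chi-square or Fisher's-exact test analysis will be used to identify variables that correlate with adverse events following anterior tethering surgery".

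Section 6.4 sets the scale: "Based on device implantation in up to 40 subjects, the study will not be sufficiently powered to gain statistical significance".

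The two sections name no estimator, interval type, list or cap of predictors, or rule for empty cells. No expected AE or SAE rate is given anywhere. One small-sample method does appear in 6.3.2: exact binomial intervals for the incidence of device-related AEs.

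On the role of this analysis, 6.3.2 says "The safety endpoint will be factors associated with the adverse events in patients that have undergone anterior VBT surgery", while 6.1 says "The primary endpoint is safety, and will consist of the rate of AEs/SAEs in anterior VBT surgery".

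**The concern.** Logistic regression without further qualification is read by default as maximum likelihood. Its estimate is not finite when a predictor, or a combination of predictors, splits events from non-events (separation). The simplest case is an empty cell in the table of event by binary factor. In 40 subjects this depends mainly on how many have the rarer outcome, so few non-events do the same harm as few events.

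Either extreme is possible here, though neither is established. Serious or device-related events may be few. An indicator for any AE could be common, because Clavien-Dindo Grades I and II count as AEs (8.3) and all AEs are recorded to day 90 (8.5).

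At stake are the promised odds ratios and intervals. If they cannot be computed, the analyst will have to drop factors, merge categories or change method after seeing the data. A plan can avoid that discretion.

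**Working it through.** **The plan's own figure.** The only computed figure is the paired t-test power in 6.4. It holds: 17.9/6.6 and 6.5/5.38 at n = 40 both give power above 99.99%, so the claim of more than 80% is true. It has no bearing on the AE regression, for which no figure is given.

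**Inputs.** N = 40, the maximum in 6.4. Event rate p is assumed from 5% to 95%. An unbalanced factor is illustrated by sex: the cited thoracoscopic series in Table 1 (section 1.3.1) has 5 males among 44, and 5/44 × 40 ≈ 5. Splits of 8/32, 12/28 and 20/20 are assumed alternatives. True effects are set to zero unless stated.

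**One binary factor.** With groups of n1 and n0, the chance of at least one empty cell is

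P = 1 − [1 − pⁿ¹ − (1−p)ⁿ¹] × [1 − pⁿ⁰ − (1−p)ⁿ⁰].

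- 5 vs 35, p = 0.10: 1 − (1 − 0.00001 − 0.5905)(1 − 0.0250) = 1 − 0.4095 × 0.9750 = 0.60.
- 8 vs 32, p = 0.10: 1 − (1 − 0.4305)(1 − 0.0343) = 0.45.

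The formula is symmetric in p and 1 − p:

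| Split | 5% or 95% | 10% or 90% | 20% or 80% | 30% or 70% | 50% |
|---|---|---|---|---|---|
| 5/35 | 81% | 60% | 33% | 17% | 6% |
| 8/32 | 73% | 45% | 17% | 6% | 1% |
| 12/28 | 65% | 32% | 7% | 1% | 0% |
| 20/20 | 59% | 23% | 2% | 0% | 0% |

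These figures include datasets with no event at all, or with an event in everyone. At p = 0.05 that alone has probability 0.95⁴⁰ = 13%.

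**One continuous predictor.** With k events and no ties, separation needs the events to hold the k highest or k lowest values, so its probability is 2/C(40, k).

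- p = 0.10: 0.0148 (k = 0) + 0.0657 × 2/40 + 0.1423 × 2/780 ≈ 1.8%.
- p = 0.05: 0.1285 + 0.2706 × 2/40 + 0.2777 × 2/780 ≈ 14%.

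**Several covariates.** Simulation, 600 datasets per setting, with a linear-programming check for separation:

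| Model | 5 / 95% | 10 / 90% | 20 / 80% | 30 / 70% | 50% |
|---|---|---|---|---|---|
| 3 covariates (2 continuous, sex 5/35) | 80 / 81% | 58 / 59% | 37 / 32% | 16 / 15% | 8% |
| 5 covariates (3 continuous, sex 5/35, one 12/28 factor) | 88 / 89% | 71 / 67% | 37 / 39% | 15 / 19% | 6% |

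A repeat with 1,500 datasets per setting agreed within about 5 percentage points.

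**Fits that did not separate.** At 5–10% or 90–95%, the median ratio of upper to lower 95% Wald limit for the last-entered binary factor was about 200 to 380 (3 covariates) and 160 to 460 (5 covariates). At 50% it was about 63 and 22.

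**Named baseline predictors.** Take Cobb angle uniform over 35–60 degrees and Sanders stages 1–4 equally likely. The two together separate in about 8 to 9% of datasets at a 10% rate, and in about a third at 5%. Adding sex (5/35) at a 10% rate raises this to between 60 and 70%.

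**What a penalised estimate gives.** Adding 0.5 to each cell equals the Firth point estimate for a 2×2 table. For AEs in 0/5 vs 4/35, OR = (0.5 × 31.5)/(5.5 × 4.5) = 0.64. SE of log OR = √(1/0.5 + 1/5.5 + 1/4.5 + 1/31.5) = 1.56, so the 95% Wald interval is 0.03 to 13.6. The mirror case, 5/5 vs 31/35, gives 1.57 (0.07 to 33.5).

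**The case against.** Five points can be made for the plan.

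- **The rates are assumed.** This stands. A reader might infer that nearly every child will have an AE, but Grade I is a departure from the normal course, so expected recovery need not count. The stopping rule in 6.6.1 acts after 15 cases only above a 50% SAE rate, so a mid-range rate is not excluded.
- **The result depends on the predictor.** This also stands. A reader might infer that any logistic model in 40 subjects will often fail. The single continuous predictor shows otherwise. A true effect matters too: with an odds ratio of 3 for the 5-subject group, the empty-cell chance falls to 26% when the reference rate is 10%, and rises to 84% when it is 90%.
- **Maximum likelihood is not named.** Correct. It is the default reading, not a commitment, and Firth or exact regression would satisfy the present wording. That is a reason to say which is meant.
- **Small-sample methods are already there.** Fisher's exact test tolerates empty cells and the device-related incidence has exact intervals. Both are sound, but neither supplies the regression odds ratios and intervals.
- **Little depends on the regression.** Largely right. The synopsis calls the analyses primarily descriptive, 6.4 concedes low power, and no stopping rule uses a coefficient. This lowers the stakes but does not withdraw the promised output. Low precision is also a different matter from an estimate that does not exist.

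**Conclusion.** The concern holds conditionally. If the modelled outcome occurs in about 10% of subjects or fewer, or 90% or more, and the model contains an unbalanced binary factor, separation is expected in roughly 45 to 89% of datasets. It is uncommon with one continuous predictor. At rates of 30 to 70% it is about 0 to 19%, and there the weakness is interval width. All these figures assume 40 subjects, null effects, and rates and covariates that the documents do not supply. Fewer subjects would make matters worse.

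A reader of 6.3.2 might infer that the trial's main safety result is undermined, because that section calls the associated factors the safety endpoint. The documents do not support this: 6.1 designates the AE/SAE rate as primary, and a rate with its exact interval is not touched by separation. The mismatch between 6.1 and 6.3.2 is a separate wording matter.

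**What to change.** In 6.3.2, with a cross-reference from 6.3.1, state that:

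- AE and SAE association models use Firth penalised-likelihood logistic regression with profile-penalised intervals, or exact logistic regression with exact intervals;
- each model has at most one or two baseline predictors named in advance, for example pre-operative thoracic Cobb angle and Sanders stage;
- results are exploratory;
- if no subject or every subject has the event, only counts are given, since no method then yields a useful odds ratio.

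The Comprehensive Complication Index, already planned in 8.3 and 8.4, may serve as a continuous outcome for overall AE burden.

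This is a cheap improvement: SAP wording and standard software, with no new data, visits or subjects. The costs are slight shrinkage of the odds ratios, fewer factors examined, and estimates that are finite but still imprecise. Limiting the predictors removes much of the problem at a 10% rate. The penalised or exact method covers what remains, chiefly at rates near 5% or 95%.

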8.4.1 Relationship of AE/SAE to study intervention or device

The relationship of each Event to the study intervention should be characterized using one of the following terms in accordance with CHOP IRB Guidelines: **definitely, probably, possibly, unlikely, or unrelated**. In this case, the “study intervention” is considered to be the surgical intervention and implantation of the medical device (*Anterior vertebral body tethering surgery under general anesthesia with spinal cord monitoring*). This includes (but is not limited to) induction of anesthesia, incision and surgical approach, device implantation, and recovery. **For each SAE, the PI and Safety Officer will make a case-by-case determination on the relationship of the SAE to the study procedure, which will be documented in the study documents.**

There will be further classification of the Event as either “device-related”, “not device-related”, or “uncertain to be device-related”. Device-related adverse events are those events directly related to the integrity, safety, or biomechanics of the implanted device. This can include variables like device breakage or device migration. Other adverse events which are considered not device-related are those that are related to the act of the surgery and medical recovery (anesthesia, incision and surgical approach, post-operative recovery, etc.). This distinction will be indicated in the study documents. **For each Event, the PI and Safety Officer will make a case-by-case determination on whether the Event is “device related”, “not device related”, or “uncertain”. An event which is classified as “device related” will be considered an Adverse Device Effect. Adverse device effects have special reporting guidelines, as outlined below.**

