8.5 Recording plan for AEs/SAEs

Surgery and Post-operative Phase (Day 0 – POD 90):

For these phases, all AEs (including SAEs) will be noted in the study records and reported per IRB and FDA requirements outlined below. The subjects will be encouraged to contact the office with any concerns, and the medical record will be monitored by study staff for indications of AEs.

Extended Follow-up Phase (POD 91-POD 730):

For this phase, all SAEs will be recorded (regardless of cause). Only AEs which are deemed “device related” will be recorded on study documents and reported per IRB and FDA requirements outlined below. The subjects will still be encouraged to contact the office with any concerns, and the medical record will be monitored by study staff for indications of SAEs or device-related AEs.

Long-term Follow-Up (POD 730 through approximately two years after skeletal maturity):

An observational study involving chart review of medical charts from CHOP and external sources as needed will be undertaken for long-term follow-up. All SAEs identified from the medical records that are considered device related, up to two years after skeletal maturity, will be reported in accordance with FDA requirements. This will be performed under a separate research protocol.

Only the AEs/SAEs indicated above will be recorded in a patient-specific study binder, kept in the secure orthopedics research office. The binder will contain a full description of the event, including the nature, date and time of onset, determination of non-serious versus serious, intensity (mild, moderate, severe), duration, causality, and outcome of the event. Hard copies of the primary documents (medical record notes) describing the event and any associated treatment will be printed and kept in the patient-specific study binder. A redundant copy of adverse events will be kept in the study REDCap database and will be maintained by the study team separately from the patient-specific study binder. The study binder will serve as the official record of all Events.

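### The only planned CI for device-related AEs leaves out the uncertain class, and after POD 90 non-serious uncertain AEs are not recorded, so the rate can be understated and only partly checked

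*Combined protocol and SAP*

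**What the plan says.** **Classification.** Section 8.4.1 has the PI and the Safety Officer judge every event: they "will make a case-by-case determination on whether the Event is “device related”, “not device related”, or “uncertain". Section 6.3.2 repeats the three classes, calling the third "uncertain to be related". It defines the first narrowly: device-related "complications will include any events directly related to the integrity, safety, or biomechanics of the Anterior Vertebral Tether Device".

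**Analysis.** Section 6.3.2 attaches an interval to one class alone: "Device-related AE incidence will be summarized along with the corresponding exact binomial 95% two-sided confidence intervals". It also promises frequencies by type, body system, severity and relationship to the study intervention, a distinction between the three device classes, and a detailed description of SAEs. No interval is planned for device-related and uncertain events together.

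**Recording.** Section 8.5 sets the rule by phase.
- Day 0 to POD 90: "For these phases, all AEs (including SAEs) will be noted in the study records".
- POD 91 to 730: all SAEs are recorded whatever their cause. Among other AEs, only those deemed device-related "will be recorded on study documents and reported per IRB and FDA requirements outlined below".

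The same section confines the patient's study binder to these classes and makes the binder the official record of events. Section 5.2, with no limit by phase, says that safety is monitored by recording all AEs and SAEs on the complication form in that same binder.

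**The concern.** An uncertain class exists because attribution to a new implant is often unsettled. If the only rate with an interval uses the events judged device-related, it depends on how doubtful events are labelled. The usual safeguard is a second rate that counts the doubtful events, so that the reader sees the range. Here that second rate is not planned, and for one group of events the data for it would not be in the AE record.

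The timing matters. Section 6.6.2 diagnoses tether failure only after 3 months, which is about when the restricted recording starts. It treats tether failure as an SAE only if the failure is noted before maturity, the Cobb angle has worsened and re-operation is required. Screw failure is also defined there by a need for re-operation. A suspected loss of tension or loosening that leads to no re-operation can therefore be non-serious. If its cause is not settled, the rule that all SAEs are recorded does not catch it.

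The study has no concurrent control group, and section 9.1 says that data go to the manufacturer for a humanitarian device exemption submission. An incomplete device-related rate would thus be read by people outside the trial.

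**Working it through.** The documents give no device-related rate, interval width or expected number of uncertain events, so there is no figure of the plan's own to reproduce. The check has two parts.

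**1. Which events can enter which rate**

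| Event, by device class | Recorded to POD 90 (8.5) | Recorded POD 91 to 730 (8.5) | In the rate with the exact CI (6.3.2) |
|---|---|---|---|
| SAE, device-related | yes | yes | yes |
| SAE, uncertain | yes | yes | no rule includes it |
| Non-serious AE, device-related | yes | yes | yes |
| Non-serious AE, uncertain | yes | **no** | no rule includes it |

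The last column is an inference. Section 6.3.2 does not say in words that uncertain events are excluded, but it keeps three separate classes and names only one for the interval. The bold cell is explicit in section 8.5. It is the only cell in which the AE record cannot supply a sensitivity analysis.

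**2. What one uncertain subject is worth**

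Inputs: n = 40 (sections 3.3.2 and 6.4, where 40 is the maximum) and a two-sided exact 95% interval (6.3.2). Let k be the number of subjects with a device-related event and u the number with only an uncertain event. Both are assumptions.

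Rate = (k + u)/n, so each subject in u adds 100/40 = 2.5 points.

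For x = k + u, the Clopper-Pearson limits are:
- lower limit: the 0.025 quantile of Beta(x, n − x + 1), or 0 if x = 0
- upper limit: the 0.975 quantile of Beta(x + 1, n − x)

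| k | u | Device-related only | Device-related plus uncertain |
|---|---|---|---|
| 0 | 2 | 0/40 = 0% (0 to 8.8%) | 2/40 = 5.0% (0.6 to 16.9%) |
| 2 | 2 | 2/40 = 5.0% (0.6 to 16.9%) | 4/40 = 10.0% (2.8 to 23.7%) |
| 4 | 1 | 4/40 = 10.0% (2.8 to 23.7%) | 5/40 = 12.5% (4.2 to 26.8%) |
| 4 | 3 | 4/40 = 10.0% (2.8 to 23.7%) | 7/40 = 17.5% (7.3 to 32.8%) |

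Over this range each added subject raises the upper limit by about 3 to 4.5 points. With fewer than 40 subjects the step is larger: at n = 20 it is 100/20 = 5 points.

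These rows show sensitivity to classification. They do not isolate unrecorded events, because u also contains uncertain SAEs and early uncertain AEs, which are on record.

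**The case against.** The strongest reply is that little is lost.

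- **Most uncertain events are kept.** All SAEs are recorded to POD 730 and all AEs to POD 90, and section 6.3.2 distinguishes the uncertain class. For those events a reader given subject-level counts can compute the second interval. This stands, and it confines the gap to non-serious uncertain AEs from POD 91 to 730.
- **Late device problems have other routes.** The synopsis lists implant failure on serial radiographs, over-correction, progression and re-operation as extended-phase endpoints. Sections 4.4.1 to 4.4.3 require spine x-rays, their abstraction and a complications review at POD 180, 365 and 730. This stands in part. Some evidence survives and could be re-read, but no such re-reading is planned, and the PI and Safety Officer's judgement on the event would not be in the AE record.
- **The primary question lies elsewhere.** Section 6.1 defines the primary endpoint as the rate of AEs/SAEs without regard to device attribution, and section 2.1 sets the objective in the early period after surgery. This stands as a limit on importance: the device-related interval is one descriptive output.
- **Section 5.2 already requires all AEs.** It does, but section 8.5 is the specific rule by phase. The two cannot both be followed after POD 90.

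A reader might infer more than the documents support. They do not show that device risk *is* understated: that requires some uncertain events to be truly device-caused, and counting all of them could overstate the risk. Nor do they show that late tether or screw problems are the ones most likely to be called uncertain. Sections 5.2 and 8.4.1 name breakage and migration as examples of device-related events. Finally, the restricted phase covers 730 − 90 = 640 of 730 days (87.7%), but that is a share of days, not of events.

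**Conclusion.** The point holds within narrow limits. The plan gives an exact interval for device-related AE incidence only, and the section 8.5 rule keeps non-serious AEs of uncertain device relation out of the official record from POD 91 to 730. The device-related rate can be understated by an unknown amount, and for those late events the AE record does not allow the usual check. Sections 5.2 and 8.5 also contradict each other on what is recorded.

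The size is 2.5 points per affected subject at n = 40. How many subjects that would be is unknown, and every count used above is assumed. The conclusion rests on reading the three classes as mutually exclusive and on section 8.5 prevailing over the general statement in section 5.2. If section 5.2 were followed instead, the recording gap would close, but the second rate would still be unplanned.

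**What to change.** 1. **Section 8.5:** for POD 91 to 730, record AEs judged device-related or uncertain, in addition to all SAEs.
2. **Sections 5.2 and 8.5:** reconcile them so that both state the same recording rule for each phase.
3. **Section 6.3.2:** report subject-level incidence with exact 95% intervals for (a) device-related events and (b), as a prespecified sensitivity analysis, device-related plus uncertain events. Count each subject once in each rate. Which rate leads is a matter of preference; reporting both is what matters.

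The cost is about one sentence in each section, slightly more AE recording in the extended follow-up phase, and a second figure that may look less favourable. The recording change should come first, because events not classified and recorded at the time cannot be reliably reconstructed later.
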